### **5.1.2 Planned number of subjects and sites**

Up to 45 subjects are anticipated to enroll in PS0018 at approximately 15 sites.

### **5.1.3 Anticipated regions and countries**

The regions planned for study conduct are Europe and North America, with possible extension to other regions and countries as required in PS0016.

## **5.2 Schedule of study assessments**

A schedule of study assessments is presented in [Table 5–1](#).

**Table 5–1: Schedule of study assessments**

Protocol activity	Visit Week a PS0018 Baseline	Open-Label Treatment Period													SFU b
		Wk 4	Wk 8	Wk 12	Wk 16	Wk 20	Wk 24	Wk 28	Wk 32	Wk 36	Wk 40	Wk 44	Wk 48/ WD		
Informed consent	X c														
Inclusion/exclusion	X d														
Physical exam e	X f												X	X	
Body weight	X f												X	X	
Vital signs g	X f	X	X	X	X	X	X	X	X	X	X	X	X	X	
Hematology/biochemistry/urinalysis h	X f		X		X		X		X		X		X	X	
12-lead ECG	X f						X						X	X	
Pregnancy testing i	X	X	X	X	X	X	X	X	X	X	X	X	X	X	
C-SSRS	X f	X	X	X	X	X	X	X	X	X	X	X	X	X	
IGRA TB test j	X f												X	X	
TB questionnaire	X f			X			X			X			X		
Blood sample for bimekizumab plasma concentrations k	X f	X	X	X	X			X			X		X	X	
Blood sample for anti-bimekizumab antibodies k	X f	X	X	X	X			X			X		X	X	
PASI	X f	X	X	X	X	X	X	X	X	X	X	X	X	X	
IGA	X f	X	X	X	X	X	X	X	X	X	X	X	X	X	
BSA	X f	X	X	X	X	X	X	X	X	X	X	X	X		
HADS	X f			X			X			X			X		
Concomitant medications	X	X	X	X	X	X	X	X	X	X	X	X	X	X	
Adverse events	X	X	X	X	X	X	X	X	X	X	X	X	X	X l	
IXRS	X	X	X	X	X	X	X	X	X	X	X	X			
Bimekizumab administration m, n	X	X	X	X m	X m	X m	X m	X m	X m	X m	X m	X m			

**Table 5–1: Schedule of study assessments**

Protocol activity	Visit Week a	PS0018 Baseline	Open-Label Treatment Period											SFU b
			Wk 4	Wk 8	Wk 12	Wk 16	Wk 20	Wk 24	Wk 28	Wk 32	Wk 36	Wk 40	Wk 44	

BSA=body surface area; C-SSRS=Columbia-Suicide Severity Rating Scale; ECG=electrocardiogram; HADS=Hospital Anxiety and Depression Scale; IGA=Investigator’s Global Assessment; IGRA=interferon gamma release assay; IXRS=interactive voice or web response system; PASI=Psoriasis Area and Severity Index; Q4W=every 4 weeks; SFU=Safety Follow-Up; TB=tuberculosis; WD= withdrawal; Wk=week

a Visit windows of ±3 days from the first dose (Baseline) at all visits except SFU, which has a window of -3 and +7 days from scheduled visit date.

b The SFU Visit will occur 20 weeks after the last dose.

c Ensure that the informed consent for PS0018 was completed by the subject (must be done before any study assessments are performed for PS0018).

d To be performed prior to the first dose of open-label bimekizumab.

e Includes evaluation of signs and symptoms of active TB and risk for exposure to TB.

f The noted PS0018 Baseline assessments will be obtained at the final visit of PS0016 and do not need to be recorded on the case report form for this study.

g Vital signs (blood pressure, pulse rate, and temperature) are to be measured prior to blood sampling and prior to dosing, where applicable.

h The FSH test should only be performed on postmenopausal females who have been postmenopausal for ≥1 year and last menstrual cycle occurred <2 year ago.

i Pregnancy testing will be urine testing at all visits except SFU, which will be a serum test.

j It is recommended that the QuantiFERON TB GOLD test be performed.

k All blood samples are to be taken prior to dosing.

l Including assessment for the development of different forms of psoriasis at the SFU visit.

m Bimekizumab will initially be administered at a dose of 160mg Q4W subcutaneously (sc) during the 48 week Open Label Treatment Period. There will be an option to increase the dose to 320mg Q4W at the discretion of the Investigator if the subject’s PASI response is ≥50% to <75% reduction from the Baseline of PS0016 at Week 12 or later. If the subject’s disease is adequately controlled on the 320mg Q4W dose, they may return to 160mg Q4W at the discretion of the Investigator. The decision to return to 160mg Q4W dosing should be based upon treatment response, tolerability, and Investigator discretion, with the aim to use the dosing regimen that achieves the optimal benefit-risk for each subject. If a subject does not achieve a PASI50 at Week 12 or later then they will be withdrawn from the study.

n Subjects should not receive their first dose in PS0018 until at least 4 weeks (+/-3 days) after their last dose in PS0016.

[figure not shown]
### 5.3 Schematic diagram

A study schematic diagram of PS0018 is presented in [Figure 5-1](#).

This document cannot be used to support any marketing authorization application and any extensions or variations thereof.

REDACTED COPY

**Figure 5–1: Schematic diagram**

BL=Baseline; PASI=Psoriasis Area and Severity Index; Q4W=every 4 weeks; sc=subcutaneously

a Bimekizumab will initially be administered at a dose of 160mg Q4W subcutaneously (sc) during the 48 week Open Label Treatment Period. There will be an option to increase the dose to 320mg Q4W at the discretion of the Investigator if the subject's PASI response is  $\geq 50\%$  to  $< 75\%$  reduction from the Baseline of PS0016 at Week 12 or later. If the subject's disease is adequately controlled on the 320mg Q4W dose, they may return to 160mg Q4W at the discretion of the Investigator. The decision to return to 160mg Q4W dosing should be based upon treatment response, tolerability, and Investigator discretion, with the aim to use the dosing regimen that achieves the optimal benefit-risk for each subject. If a subject does not achieve a PASI50 at Week 12 or later then they will be withdrawn from the study.

## 5.4 Rationale for study design and selection of dose

PS0018 is a 48-week open-label extension study for eligible subjects who participated in PS0016, a Phase 2a, randomized, subject-blind, Investigator-blind study in adult subjects with moderate to severe chronic plaque psoriasis. This study will allow the collection of further data on the long-term safety, tolerability, and efficacy of bimekizumab in this subject population and will provide continued access to bimekizumab.

Bimekizumab will initially be administered at a dose of 160mg Q4W subcutaneously (sc) during the 48 week Open Label Treatment Period. There will be an option to increase the dose to 320mg Q4W at the discretion of the Investigator if the subject's PASI response is  $\geq 50\%$  to  $< 75\%$  reduction from the Baseline of PS0016 at Week 12 or later. If the subject's disease is adequately controlled on the 320mg Q4W dose, they may return to 160mg Q4W at the discretion of the Investigator. The decision to return to 160mg Q4W dosing should be based upon treatment response, tolerability, and Investigator discretion, with the aim to use the dosing regimen that achieves the optimal benefit-risk for each subject. If a subject does not achieve a PASI50 at Week 12 or later then they will be withdrawn from the study.

The rationale for the selection of the 160mg Q4W dose for this study is based on the following:

- The optimal therapeutic dose of bimekizumab will not yet be known at the time subjects begin entering PS0018 from PS0016.
- The 160mg Q4W dose is within the range of doses that have already been explored by iv administration. This dose was selected based on modeling using the currently available data and may be modified, if appropriate, as further data are collected on the optimal dose of bimekizumab.
- The 160mg Q4W starting dose in PS0018 will provide data to evaluate the safety and efficacy of a dose reduction.

## 6 SELECTION AND WITHDRAWAL OF SUBJECTS

### 6.1 Inclusion criteria

To be eligible to participate in this study, all of the following criteria must be met:

1. An Institutional Review Board (IRB)/Independent Ethics Committee (IEC) approved written Informed Consent form is signed and dated by the subject.
2. Subject is considered reliable and capable of adhering to the protocol and visit schedule according to the judgment of the Investigator.
3. Subject completes all dosing requirements in PS0016 without meeting any withdrawal criteria.
4. **Female** subjects must be postmenopausal (at least 1 year; to be confirmed hormonally at the PS0018 Baseline Visit, if less than 2 years since last menstrual period), permanently sterilized (eg, tubal occlusion, hysterectomy, bilateral salpingectomy) or, if of childbearing potential, must be willing to use a highly effective method of contraception up until 20 weeks after last administration of study medication (anticipated 5 half-lives), and have a negative

pregnancy test at Visit 1 (Baseline) and immediately prior to first dose. The following methods are considered highly effective when used consistently and correctly:

- combined (estrogen and progestogen) hormonal contraception associated with inhibition of ovulation (oral, intravaginal, or transdermal)
- progestogen-only hormonal contraception associated with inhibition of ovulation (oral, injectable, or implantable)
- intrauterine device
- intrauterine hormone-releasing system
- bilateral tubal occlusion
- vasectomized partner
- sexual abstinence if it is in accordance with a subject's preferred and common lifestyle. Subjects who use abstinence as a form of birth control must agree to abstain from heterosexual intercourse until 20 weeks after the last dose of study medication. Study personnel must confirm the continued use of abstinence is still in accordance with the subject's lifestyle at regular intervals during the study.

**Male** subjects with a partner of childbearing potential must be willing to use a condom when sexually active, up till 20 weeks after the last administration of study medication (anticipated 5 half-lives).

## 6.2 Exclusion criteria

Subjects are not permitted to enroll in the study if any of the following criteria are met:

1. Subject has previously participated in this study.
2. Female subjects who plan to become pregnant during the study or within 20 weeks following last dose of study medication. Male subjects who are planning a partner pregnancy during the study or within 20 weeks following the last dose.
3. Subject has any medical or psychiatric condition that, in the opinion of the Investigator, could jeopardize or would compromise the subject's ability to participate in this study. Note: For any subject with an ongoing serious adverse event (SAE), or a history of serious infections (including herpes zoster or hospitalizations) in PS0016, the Medical Monitor must be consulted prior to the subject's entry into PS0018.
4. Subject has any current sign or symptom that may indicate a medically significant infection.
5. Subject has current clinically active infection with Histoplasma, Coccidioides, Paracoccidioides, Pneumocystis, tuberculosis (TB), nontuberculous mycobacteria (NTMB), Blastomyces, Aspergillus, or Candidiasis (systemic). Any subject diagnosed with Histoplasmosis, Coccidioides, Paracoccidioides, Pneumocystis, TB, NTMB, Blastomyces, Aspergillus, or Candidiasis (systemic) during PS0016 is excluded from PS0018 even if treatment has been completed.
6. Any subject who meets any withdrawal criteria in the feeder study (PS0016) is excluded from participating in the open-label extension study (PS0018).

### 6.3 Withdrawal criteria

Subjects are free to withdraw from the study at any time, without prejudice to their continued care.

Subjects should be withdrawn from the study and will be asked to complete the Early Withdrawal Visit and SFU Visit (20 weeks after the last received dose) if any of the following events occur:

1. Subject withdraws his/her consent.
2. There is confirmation of a pregnancy in a female subject during the study, as evidenced by a positive pregnancy test.
3. The Sponsor or a regulatory agency requests withdrawal of the subject.
4. Subject develops an illness that in the opinion of the Investigator would interfere with his/her continued participation if the risk of continuing participation outweighs the potential benefit.
5. Subject develops erythrodermic, guttate, or pustular form of psoriasis.
6. Subjects considered to have either a suspected new latent tuberculosis (LTB) infection or who develop an active TB or NTMB infection during the study (including but not limited to, conversion demonstrated by interferon-gamma release assay [IGRA] or other diagnostic means) must be immediately discontinued from study medication; an Early Withdrawal Visit must be scheduled as soon as possible, but not later than the next regular visit.

Confirmed active TB is an SAE and must be captured on an SAE Report Form and provided to the Sponsor in accordance with SAE reporting requirements. As with all SAEs, periodic follow-up reports should be completed as per protocol requirements until such time as the TB infection resolves.

7. Subject is noncompliant with the study procedures or medications in the opinion of the Investigator.
8. Subject uses prohibited concomitant medications that may present a risk to the safety of the subject in the opinion of the Investigator and/or the Medical Monitor.
9. Subject experiences an AE as described below:
  - Any Common Terminology Criteria for Adverse Events (CTCAE) Grade 3 and above AE that is assessed as related to study drug in the opinion of the Investigator.
    - If the event is deemed to be not related to study drug by the Investigator, the subject may remain in the study after approval by the Medical Monitor.
  - Any CTCAE Grade 2 event that is evaluated as related to study drug in the opinion of the Investigator, is persistent, and falls into any of the following system organ classes (SOCs): “Blood and lymphatic disorders,” “Cardiac disorders,” or “Vascular disorders.”
    - Persistent is defined as lasting 28 days or more, which spans at least 2 scheduled injections.

10. Subject has a clinical laboratory value meeting the following criteria:

- CTCAE Grade 3 and above: subjects must be withdrawn regardless of relationship to study drug or duration of event.
- CTCAE Grade 2
  - Subjects may remain in the study if the event is transient. If a subject has a Grade 2 laboratory abnormality, a retest is required within 1 to 2 weeks at a scheduled or unscheduled visit. If the repeat value is below Grade 2, the subject may receive the next scheduled study treatment. If the value on the repeat is still Grade 2 or above, a second repeat test must be performed and results made available prior to the next scheduled study treatment. If this second repeat value is still Grade 2 or above, the subject must be withdrawn.

11. Subject has active suicidal ideation as indicated by a positive response (“Yes”) to questions 4 or 5 or to the suicidal behavior questions of the “Since Last Visit” version of the self-rated Columbia-Suicide Severity Rating Scale (C-SSRS). The subject should be referred immediately to a Mental Healthcare Professional and must be withdrawn from the study.

12. Subjects with a HADS-D score  $\geq 15$  must be withdrawn. Any subject who develops a HADS-D score of  $>10$  during the study should be referred immediately to a Mental Healthcare Professional for further evaluation and potential withdrawal by the Investigator.

13. Subject does not achieve a PASI50 at Week 12 or later following open-label treatment in PS0018.

14. Subjects with newly diagnosed Inflammatory Bowel Disease (IBD) or with IBD flares during the study must:

- Be referred, as appropriate, to a healthcare professional treating IBD, such as a gastroenterologist
- Discontinue the IMP and be followed-up until resolution of active IBD symptoms

If IBD flares increase in severity or frequency during the study, the Investigator should use clinical judgment in deciding whether the subject should continue in the study and contact the Medical Monitor and UCB study physician to confirm the subject's suitability for continued participation in the study.

Investigators should attempt to obtain information on subjects in the case of withdrawal. For subjects considered as lost to follow-up, the Investigator should make an effort (at least 1 phone call and 1 written message to the subject), and document his/her effort (date and summary of the phone call and copy of the written message in the source documents), to complete the final evaluation. All results of these evaluations and observations, together with a narrative description of the reason(s) for removing the subject, must be recorded in the source documents. The eCRF must document the primary reason for withdrawal.

Investigators should contact the Medical Monitor, whenever possible, to discuss the withdrawal of a subject in advance.

### 6.3.1 PDILI IMP discontinuation criteria

Subjects with potential drug-induced liver injury (PDILI) must be assessed to determine if investigational medicinal product (IMP) must be discontinued. In addition, all concomitant medications and herbal supplements that are not medically necessary should also be discontinued.

The PDILI criteria below require immediate and permanent discontinuation of IMP:

- Subjects with either of the following:
  - ALT or AST  $\geq 5xULN$
  - ALT or AST  $\geq 3xULN$  and coexisting total bilirubin  $\geq 2xULN$
- Subjects with ALT or AST  $\geq 3xULN$  who exhibit temporally associated symptoms of hepatitis or hypersensitivity. Hepatitis symptoms include fatigue, nausea, vomiting, right upper quadrant pain or tenderness. Hypersensitivity symptoms include fever (without clear alternative cause), rash, or eosinophilia (ie,  $>5\%$ ).

The PDILI criterion below allows for subjects to continue on IMP at the discretion of the Investigator.

- Subjects with ALT or AST  $\geq 3xULN$  (and  $\geq 2x$  baseline) and  $< 5xULN$ , total bilirubin  $< 2xULN$ , and no eosinophilia (ie,  $\leq 5\%$ ), with no fever, rash, or symptoms of hepatitis (eg, fatigue, nausea, vomiting, right upper quadrant pain or tenderness).

Evaluation of PDILI must be initiated as described in Section 9.7.1. If subjects are unable to comply with the applicable monitoring schedule, IMP must be discontinued immediately.

Investigators should attempt to obtain information on subjects in the case of IMP discontinuation to complete the final evaluation. Subjects with PDILI should not be withdrawn from the study until investigation and monitoring are complete. All results of these evaluations and observations, as well as the reason(s) for IMP discontinuation and subject withdrawal (if applicable), must be recorded in the source documents. The eCRF must document the primary reason for IMP discontinuation.

## 6.4 Study stopping rules

During the study, planned dosing and procedures may be discontinued or suspended for all subjects in any part of the study and appropriate follow up procedures established. Where it is possible to do so without threatening the safety of subjects, such discontinuation/suspension should be discussed with the UCB Study Physician prior to its implementation.

Possible reasons for discontinuation or suspension of the study include (but are not limited to):

- A pattern of AEs occurs that contraindicates the further dosing of enrolled / additional subjects, including (but not limited to):
  - More than 1 subject meets any individual Withdrawal Criteria 6, 9, 10, 11 or 12 (as provided in Section 6.3), regardless of whether they met the same or different criteria.
  - Once a second subject meets any of those criteria, referral to the DMC may not be delayed while awaiting the outcome of either case.

If the above criteria are reached, the DMC will meet as soon as possible to determine whether discontinuation or suspension of the study should occur, and to determine what investigations, analyses, procedural amendments, or other actions should occur, before making any recommendation regarding the possibility of recommencing the study. Further details on the role of the DMC are provided in [Section 9.8.7](#).

- If the Sponsor or its designees judges it necessary for medical, safety, regulatory, or any other reasons consistent with applicable laws, regulations, and GCP.

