### 9.5 Adverse events of special interest

An AE of special interest is any AE that a regulatory authority has mandated be reported on an expedited basis, regardless of the seriousness, expectedness, or relatedness of the AE to the administration of a UCB product/compound.

Potential Hy’s Law, defined as  $\geq 3 \times \text{ULN}$  ALT or AST with coexisting  $\geq 2 \times \text{ULN}$  total bilirubin in the absence of  $\geq 2 \times \text{ULN}$  ALP, with no alternative explanation for the biochemical abnormality, must ALWAYS be reported to UCB as an AE of special interest (ie, without waiting for any additional etiologic investigations to have been concluded). Follow-up information should then be reported if an alternative etiology is identified during investigation and monitoring of the subject.

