**Table 9-3: Required investigations and follow-up for PDILI**

Laboratory value		Symptoms a of hepatitis or hypersensitivity	Immediate		Follow up	
ALT or AST	Total bilirubin		Consultation requirements	Actions	Testing	Evaluation
≥3xULN	≥2xULN b	NA	Hepatology consult. c Medical Monitor must be notified within 24 hours (eg, by laboratory alert) and subject discussed with Medical Monitor ASAP.	Immediate, permanent IMP discontinuation.	Essential. Must have repeat liver chemistry values and additional testing completed ASAP (see Section 9.7.1.3 ); recommended to occur at the site with HCP.	Monitoring of liver chemistry values at least twice per week until values normalize, stabilize, or return to within baseline values. d
≥3xULN	NA	Yes				
≥5xULN	NA	NA	Need for hepatology consult to be discussed (required if ALT or AST ≥8xULN). Medical Monitor must be notified within 24 hours (eg, by laboratory alert) and subject discussed with Medical Monitor ASAP.			

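### The automatic two-subject DMC referral in Protocol 6.4 omits the 6.3.1 liver stops, so ALT/AST of 3 to 5xULN with bilirubin of 2 to 3xULN does not count at onset

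*Protocol*

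**What the plan says.** Protocol 6.4 gives an open-ended list of reasons to suspend or stop the study. One event on it is counted by number: "More than 1 subject meets any individual Withdrawal Criteria 6, 9, 10, 11 or 12 (as provided in Section 6.3". The subjects need not meet the same criterion. The next line protects the timing: "Once a second subject meets any of those criteria, referral to the DMC may not be delayed while awaiting the outcome of either case". The DMC then meets as soon as it can and decides what to do. Reaching the trigger does not itself suspend dosing.

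The liver rules sit apart, in 6.3.1, without numbers: "The PDILI criteria below require immediate and permanent discontinuation of IMP". They cover ALT or AST at or above 5xULN, at or above 3xULN with bilirubin at or above 2xULN, and at or above 3xULN with symptoms of hepatitis or hypersensitivity.

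Two numbered criteria in 6.3 can bring a liver case into the count:

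- Criterion 9 takes any "Grade 3 and above AE that is assessed as related to study drug in the opinion of the Investigator". Its Grade 2 limb is confined to persistent, related events in the blood, cardiac and vascular classes.
- Criterion 10 covers laboratory values: "CTCAE Grade 3 and above: subjects must be withdrawn regardless of relationship to study drug or duration of event". For Grade 2 it asks for a retest within 1 to 2 weeks and a second repeat before the next dose. "If this second repeat value is still Grade 2 or above, the subject must be withdrawn".

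Under Protocol 9.5, potential Hy's Law "must ALWAYS be reported to UCB as an AE of special interest". No DMC trigger is attached to that report.

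**The concern.** Safety is the primary objective, and liver enzyme changes are listed for special monitoring in 9.6. The trigger in 6.4 takes five kinds of event out of anyone's discretion and forbids waiting to see how they turn out. A liver pattern serious enough for a permanent stop is not among them.

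The resulting order of priority is hard to defend. Two subjects with an isolated Grade 3 total cholesterol or GGT reach the DMC as soon as the results are known, whatever the cause. Two subjects permanently stopped at ALT 4xULN with bilirubin 2.5xULN do not. Because the trigger adds up across criteria, one such liver case plus one subject with, say, a criterion 11 event also falls short of two.

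**Working it through.** There is no planned figure to reproduce. The check sets the stop limits against the counting limits.

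**Inputs**

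- Permanent stop (Protocol 6.3.1): ALT/AST ≥5xULN; or ≥3xULN with bilirubin ≥2xULN; or ≥3xULN with symptoms.
- Grade 3 and above (SAP Table 14-2): ALT/AST >5.0xULN; bilirubin >3.0xULN; GGT >5.0xULN; total cholesterol >10.34 mmol/L.
- Criterion 10 at onset: met only by a Grade 3 or higher value.

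**Step 1: who counts at onset through criterion 10**

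| Values | 6.3.1 permanent stop | Grade 3 | Counted at onset |
|---|---|---|---|
| ALT/AST 5.1xULN, bilirubin 1xULN | yes | yes | yes |
| ALT/AST 4xULN, bilirubin 3.1xULN | yes | yes | yes |
| ALT/AST 3xULN, bilirubin 2xULN | yes | no | no |
| ALT/AST 4xULN, bilirubin 2.5xULN | yes | no | no |
| ALT/AST 4xULN, bilirubin 1xULN, symptoms | yes | no | no |
| Total cholesterol >10.34 mmol/L alone | no | yes | yes |
| GGT >5.0xULN alone | no | yes | yes |

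The uncounted band is ALT/AST from 3 to 5xULN with bilirubin from 2 to 3xULN, plus the symptomatic 3 to 5xULN cases with bilirubin up to 3xULN. A value of exactly 5.0xULN is a stop but not Grade 3. This step needs no Grade 2 limit: the band is below Grade 3 wherever Grade 2 begins.

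**Step 2: criterion 9.** A case in the band counts at onset if the Investigator records a Grade 3 or higher adverse event and judges it related. That is a judgement, not an automatic count. The Grade 2 limb contains no hepatic class.

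**Step 3: when the band counts later.** The documents give no Grade 2 limits, so calling these values Grade 2 is an assumption. If they are, both repeats must remain at Grade 2 or above.

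- If the liver monitoring samples serve as the repeats: Table 9-3 requires a repeat as soon as possible, then "Monitoring of liver chemistry values at least twice per week until values normalize, stabilize, or return to within baseline values". At 2 samples per week, 2 repeats take 2 / 2 = 1 week.
- On criterion 10's own timetable: first retest at 1 to 2 weeks, second before the next scheduled dose. For a sample drawn at a dosing visit, the next dose is nominally 4 x 7 = 28 days later (24 to 32 days under 7.2).

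The documents do not say which timetable applies.

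**Step 4: when it never counts by this route.** If either repeat is below Grade 2, criterion 10 does not require withdrawal. A subject who improves once the drug is stopped drops out of the count, so counting depends on the outcome.

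**Step 5: is it potential Hy's Law?** Under 9.5 it is, if ALP is below 2xULN and nothing else explains the values.

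**The case against.** The strongest reply is that the list in 6.4 is open. Two liver stops could be referred as a pattern of adverse events, and the sentence convening the DMC can be read to cover such a pattern. This stands, and it removes any claim that the DMC cannot be told. It does not supply an automatic count, which is what 6.4 provides for the other criteria.

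Second, criterion 10 could be read as met by any single Grade 2 value, since Grade 2 appears as one of its limbs. Its text tells against this: a subject with a transient Grade 2 value may stay, and withdrawal follows only the second repeat.

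Third, the separation may be deliberate. 6.3.1 governs stopping the drug, and PDILI subjects are kept in the study until the work-up is complete, whereas 6.4 counts withdrawal criteria. Other criteria, such as 5 and 14, are also left out. That explains the structure, but neither document gives a reason for leaving liver stops out of the referral count.

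Fourth, liver cases have other safeguards. PDILI events reach the sponsor within 24 hours (9.7.1), and potential Hy's Law is an example of an important medical event (9.2.1). Table 9-3 brings in the Medical Monitor and hepatology, and SAP 14.3.8 refers to adjudication of possible drug-induced liver injury. The DMC also reviews safety periodically (9.1.9). All of this stands and limits the harm. Earlier liver test increases had no convincing relationship to exposure (2.2.1).

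Fifth, counting every symptomatic ALT/AST value of 3xULN or more could convene the DMC for nonspecific findings. Fatigue, rash and eosinophilia above 5% all qualify, and Protocol 2.1 names fatigue as an effect of psoriasis. This is a fair point and narrows the fix.

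**Conclusion.** The gap is real but narrow. For ALT/AST of 3 to 5xULN with bilirubin of 2 to 3xULN, the plan stops the subject's drug permanently yet does not count the case towards DMC referral at onset, unless a related Grade 3 or higher adverse event is recorded. The automatic count comes about 1 week later, or as late as the next scheduled dose, or not at all if a repeat falls below Grade 2. What is lost is the automatic count and the bar on delay.

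Three stronger readings are tempting and unsupported:

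- That all 6.3.1 stops escape the trigger. They do not: ALT/AST above 5xULN or bilirubin above 3xULN counts at once.
- That such cases would go unnoticed. Sponsor reporting and liver monitoring are already required.
- That the gap can be measured in doses given to other subjects. The trigger only convenes the DMC, so no number of preventable doses follows, and the documents give no frequency for these values.

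The conclusion at onset assumes that criterion 10 is graded as in SAP Table 14-2. The delay also assumes the values are Grade 2 and depends on which samples count as repeats. The DMC charter and DMC SAP are separate documents; a liver trigger in either could close the gap.

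**What to change.** In the two-subject bullet of 6.4, after the reference to Section 6.3, add as a further counted event the 6.3.1 criterion of ALT or AST ≥3xULN together with total bilirubin ≥2xULN. Leave the rest of the bullet unchanged, so that liver cases still add to cases under the other criteria and the bar on delay applies to them.

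Adding the symptomatic ALT/AST ≥3xULN criterion is optional; the sponsor should weigh it against its nonspecific symptoms.

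No new tests, visits or subjects are needed, because the liver values and the 24-hour report are already required. The cost is a protocol amendment with sponsor and IRB/IEC approval, and regulatory approval if required (15.5), plus a possible extra ad hoc DMC meeting. If the DMC charter already holds an equivalent trigger, a cross-reference in 6.4 would be enough.
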